### 4. INTERVENTION

The intervention is designed to complement medical management. Therefore, all patients will continue to be medically managed by their health care provider as usual.

Participants will have a visit at baseline and Month 3 (with some flexibility to do the final visit at 3 months +/- 1 month) coordinated with their regular clinic visits that are typically scheduled every 3 months.

**Vitamin C supplementation.** Throughout the study, patients will continue with their routine diets. Patients randomized to the intervention groups will be provided with 4-month supply of either Vitamin C 500mg or Vitamin C tablets (1000mg) in a bottle and the control group will be provided placebo tablets in a bottle. All participants in the intervention group will be instructed to take one vitamin C tablet (500mg/ day or 1000mg/day) with one meal daily from baseline for 3 months and all control group participants will be instructed to take one placebo tablet with one meal daily from baseline to 3 months. Participants will return their un-used investigational drugs on the day of their 3-month follow-up. We will count remaining pills to determine participant's treatment adherence with both the vitamin C supplementation (500mg or 1000mg) and control (placebo) groups. After counting the pills, the un-used pills will be delivered to the Investigational Drug Services (IDS) pharmacy to dispose. We will draw blood to measure serum vitamin C level to determine drug accountability.

**Role of the Investigational Drug Services (IDS).** The IDS will provide oversight for the storage, dispensing, labeling, distribution and disposal of all investigational medications (vitamin C tablets and placebo) for the study.

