### 3. INVESTIGATIONAL PLAN

**Design.** This project is a feasibility pilot study to test the effects of vitamin C supplementation, and to obtain initial estimates of effect size to support a future RCT. The proposed vitamin C supplementation intervention study is a three-group, single blind, placebo controlled prospective design (control n=14, Vit C 500mg n=14, Vit C 1000mg n=14). The most commonly tested dose of vitamin C in current trials on vitamin C supplementation is 1 g/day. The primary endpoint to evaluate the effect of vitamin C supplementation is serum vitamin C level. The secondary outcomes include HF symptom burden, HRQOL, cardiac function, and oxidative stress. The variables would be measured in person at baseline and at 3 months include: HF symptom burden, HRQOL, PROMIS fatigue, depression and sleep disturbance, serum vitamin C level, biomarker of cardiac function (i.e., cardiac output using impedance cardiograph) and oxidative stress (8-iso-PGF2a isoprostane, see below in detail), as well as demographic, clinical, and other variables that can affect study outcomes (e.g., age, gender, race/ethnicity, body mass index, serum creatinine) and medications. HF symptom burden and HRQOL will also be measured at Month 1 and 2 by phone. We will also collect data to assess feasibility (recruitment, retention, attrition rates).

**Sample and Setting.** A total of 42 participants (14 per group) will be randomly assigned to either the control or the intervention group. Patients with HF will be recruited at the University of North Carolina Hospital internal medicine/cardiology outpatient clinics.

**Inclusion/Exclusion Criteria.** Inclusion criteria include patients (a) have a diagnosis of chronic HF. The diagnosis and etiology of chronic HF will be confirmed by a HF cardiologist using established criteria, (b) have undergone evaluation of HF and optimization of medical therapy, (c) are not taking any vitamin C supplementation at all or are willing to stop taking their current vitamin C supplementation, (d) able to read and speak English, (e) have >1 month from any inpatient hospitalization, (e) treating cardiology healthcare provider indicates the individual is a good candidate for this study that involves 3 months of vitamin C supplement of 500 mg/day, 1g/day, or placebo, (f) Per treating healthcare provider's assessment, patient's projected lifespan is greater than or equal to 6 months.

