**Follow up phone call (Month 1 and 2).** Follow up phone calls will occur within 1 week after enrollment to follow-up whether they are taking the investigational pills (vitamin C or placebo) daily and whether they have any adverse events from taking the investigational pills, as well as at Month 1 and 2. The research assistant will inquire about general welfare and collect data on HF symptom burden and HRQOL (for both groups).

***Month 3 visit.*** Data on socio-demographics, clinical characteristics medications, symptom burden, PROMIS depression, fatigue, and sleep disturbance, HRQOL, will be collected at the beginning of the visit and blood will be drawn to measure serum vitamin C level and oxidative stress (8-iso-PGF2a isoprostane). All participants will be asked to return their vitamin C (or placebo) bottle to the research assistant at Month 3. We will count pills to determine their adherence to taking the placebo or vitamin C supplementation.

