## 7. MEASUREMENTS AND STUDY EVALUATIONS

**Serum vitamin C level.** We will measure participant's serum vitamin C level at baseline and Month 3 to measure the effect of vitamin C supplementation. Sample vitamin C will be measured in serum using MyBioSource ELISA kits.

**Symptom burden.** Physical symptom burden will be measured using items from the Memorial Symptom Assessment Scale—Heart Failure (MSAS-HF). The MSAS-HF is an 8-item questionnaire adapted from Portney's Memorial Symptom Assessment Scale that is designed to provide multidimensional information about HF symptoms experienced by patients with HF. Patients will be first asked if the symptom was present during the previous 7 days. If present, three characteristics of each symptom will be rated: frequency of symptom, severity of symptom, and degree of symptom distress. Frequency is rated on a scale from 1 to 4 (rarely to almost constantly), severity rated on a scale from 1 to 4 (mild to very severe) and distress rated on a scale from 0 to 4 (not at all to very severe). Burden score for each symptom can range from 0 (no burden) to 12 (greatest symptom frequency, severity, and distress). The scale has good reliability, ranges of 0.73-0.92 in patients with HF.

**Health-related quality of life (HRQOL).** The Minnesota Living with Heart Failure questionnaire (MLHFQ) is a measure of HRQOL that assesses the patient's perceptions of the

influence of HF on physical and emotional aspects of life. The 21 items are summed with higher scores indicating worse HRQOL. The questionnaire has been widely used to measure quality of life in this population. Researchers have demonstrated evidence for validity and reliability (Cronbach's alphas ranging from .88 to .93). The MLHFQ was used in our study that demonstrated a significant relationship between vitamin C deficiency and HRQOL, as well as between HRQOL and re-hospitalization or mortality.

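### Tablets are instructed for 3 months, but the only post-baseline serum vitamin C sample may be drawn as late as Month 4; the dosing instruction should run to the blood draw

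*Combined protocol and SAP*

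**What the plan says.** **Dosing.** Section 4 (Intervention) instructs participants in the vitamin C arms to take one tablet "with one meal daily from baseline for 3 months". The placebo sentence that follows sets the same end, worded as a period running up to 3 months. The eligibility text in Section 3 repeats the duration: the treating provider is asked whether the patient suits "this study that involves 3 months of vitamin C supplement of 500 mg/day", the 1 g dose or placebo.

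**Visit.** Section 4 ties the final visit to routine clinic appointments, "with some flexibility to do the final visit at 3 months +/- 1 month".

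**Sampling.** Section 7 states: "We will measure participant's serum vitamin C level at baseline and Month 3". The Month 3 paragraph of Section 5 says that "blood will be drawn to measure serum vitamin C level and oxidative stress". No other post-baseline blood draw is planned. Section 9 names serum vitamin C as the primary endpoint.

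**Supply and return.** Participants in the vitamin C arms "will be provided with 4-month supply"; the size of the placebo supply is not given. Section 4 adds: "Participants will return their un-used investigational drugs on the day of their 3-month follow-up", and: "We will count remaining pills to determine participant's treatment adherence".

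**Contacts.** Section 8 schedules calls within 1 week of enrollment and at Months 1 and 2. The checklist in Section 10 also has a Month 3 entry, but it covers adverse events only.

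**The concern.** The instruction gives dosing a fixed length, while the visit that supplies the primary endpoint can move a month either way. A participant who follows the instruction exactly and is seen late has already stopped tablets when blood is drawn. In the vitamin C arms, any fall in serum level after stopping would make supplementation look less effective than it was. Stopping placebo has no matching effect, so the error would run one way, toward no difference. The isoprostane sample comes from the same draw.

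This matters mainly because Section 3 gives the pilot the job of supplying initial effect-size estimates for a later randomized trial. Section 4 also uses the serum level to judge drug accountability, so a participant who obeyed the instruction could be read as non-adherent.

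**Working it through.** **Inputs.** Instructed dosing ends at Month 3 (Section 4). The final visit V lies between Month 2 and Month 4 (Section 4, 3 ± 1). There is one post-baseline serum sample, at V (Sections 5 and 7). The vitamin C supply is 4 months (Section 4). The last scheduled call is at Month 2 (Section 8).

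**Step 1: time off tablets at the draw.** On the literal reading, gap = max(0, V − 3).

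- V = 2: gap 0
- V = 3: gap 0
- V = 4: gap 4 − 3 = 1 month, about 30 days

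If dosing runs to the visit, the gap is 0 for every V and treatment lasts V, that is, 2 to 4 months. The early half of the window therefore gives shorter exposure but no off-tablet sample. The vitamin C supply covers the latest visit on either reading.

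**Step 2: would the pill count show which reading was followed?** Assume 30-day months and one tablet daily, so the supply is 4 × 30 = 120 tablets. A fully adherent participant who stops at day 90 returns 120 − 90 = 30 at any later visit.

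| Visit | Left if dosed fully to the visit | Excess if stopped at day 90 | Adherence to the visit that also leaves 30 |
|---|---|---|---|
| Day 97 | 120 − 97 = 23 | 30 − 23 = 7 | 90/97 = 92.8% |
| Day 104 | 120 − 104 = 16 | 30 − 16 = 14 | 90/104 = 86.5% |
| Day 120 | 120 − 120 = 0 | 30 − 0 = 30 | 90/120 = 75.0% |

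Thirty tablets returned at Month 4 would be noticed, but the count alone cannot separate an instructed stop from missed doses. Section 4 gives no denominator for adherence, and the Section 10 checklist does not ask when the last tablet was taken.

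**Step 3: can the bias be sized?** The proportional loss in an arm's mean contrast would be roughly a × b × c. Here a is the share of the arm seen late, b the share of those who stopped at Month 3, and c the average share of the effect lost by the draw. The documents give none of the three. If a or b is zero, the bias is zero.

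**Step 4: the plan's power figure.** Section 9 states 80% power with 14 per group, alpha .05 and effect size 0.5. Reading 0.5 as Cohen's f, a one-way ANOVA with 2 and 39 degrees of freedom and noncentrality 42 × 0.5² = 10.5 gives 80.3%, so the figure reproduces. The section does not tie that effect size to serum vitamin C, so it cannot be used to turn the timing gap into lost power. Correcting the wording leaves the sample size and this figure unchanged.

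**The case against.** The strongest reply is that the plan uses its 3-month wording as the name of the final visit, flexibility included, and not as a calendar day. Unused tablets come back at what Section 4 calls the 3-month follow-up. The placebo sentence runs parallel to the baseline-to-follow-up phrasing used in Sections 2 and 9. The 4-month supply equals the latest permitted visit, so on the literal reading the fourth month of tablets would be spare stock. Harm also needs three things together: a late visit, a participant who stops with tablets in hand, and a material fall in level before the draw. The consent form and bottle labels, which carry what participants are told, cannot be seen here.

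Most of this stands. Dosing to the visit was probably intended, and the unseen materials may say so. It does not remove the point. The text available states a duration, Section 3 repeats it in what the provider approves, and nothing visible tells participants to continue until a late visit. The last scheduled call comes a month before the stated stop. If participants do continue to a late visit, their exposure exceeds the 3 months written in Sections 3 and 4, so the wording needs correcting on either reading.

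A reader might go further and infer that the primary endpoint is biased, or that the trial will lose a definite amount of power. The documents do not support either: they show no late visits, no early stopping and no rate of decline.

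**Conclusion.** The point holds as a minor mismatch between a stated dosing rule and the visit window. Taken literally, the rule permits the only post-baseline primary-endpoint sample to be drawn up to about one month after the last instructed tablet. The direction of any effect is toward zero in the vitamin C versus placebo contrast, assuming that serum levels fall once tablets stop. If participants dose to the visit, there is no bias. Visits at or before Month 3 are unaffected on either reading, and so are participants whose final assessment is remote under Section 6, because no blood is then drawn.

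No percentage for dilution or lost power should be quoted, since it would rest wholly on assumed inputs. The point is worth acting on because correction costs so little, not because harm has been shown.

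**What to change.** - **Section 4:** in all three arms, replace the 3-month instruction with *one tablet daily until the day of the final blood draw (up to 4 months)*. The 4-month limit also gives a stopping point if the final assessment is remote.
- **Section 3:** align the 3-month duration in the provider-approval criterion (the second one lettered e), so that approval covers up to 4 months.
- **Supply:** confirm that placebo is also dispensed for 4 months. No extra vitamin C tablets are needed.
- **Final-visit form:** record the date and time of the last tablet, for example on the Month 3 entry of the Section 10 checklist.
- **Consent form and labels:** use the same wording if they now say 3 months.

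The cost is one sentence, one phrase and two form entries. Sample size, visits and analysis do not change.

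There are two downsides. Treatment duration varies openly from 2 to 4 months, as the window and supply already allow. A participant seen at Month 4 may also take tablets for up to 4 − 2 = 2 months after the last scheduled safety call.

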## **5. PROCEDURES AND RECRUITMENT STRATEGY**

Permission for this study will be obtained from the University of North Carolina at Chapel Hill Institutional Review Board. A dedicated and trained research assistant will recruit HF patients from the UNCH clinics. A list of HF patients who will come to the UNCH clinics will be generated and obtained from the staff in charge for the scheduling information in the clinics one week before patients' visits. On the day that the potential participants come to the clinic, the research assistant will screen the potential participant's eligibility based on inclusion and exclusion criteria. The research assistant also will consult with the potential participant's treating healthcare provider to make sure the potential participant is appropriate for the study and patient's projected lifespan is greater than or equal to 6 months. Once the research assistant confirms the potential participants are eligible and gets approval from the provider, the research assistant will approach and briefly explain the study to recruit potential participants while they wait to see their physicians. If potential participants are interested in participation, the research assistant will then confirm eligibility. For eligible patients, study requirements will be explained in detail. If the patient agrees to participate, a signed informed consent will be obtained based on consent process (see below) and we will administer the survey, measure cardiac impedance and obtain the blood samples. All eligible patients will be randomized to either the control group or to the intervention group using the Medsharing application for clinical trials.

**Baseline visit.** Data on socio-demographics, clinical characteristics medications, symptom burden, PROMIS depression, fatigue, and sleep disturbance, HRQOL, will be collected at the beginning of the visit and blood will be drawn to measure serum vitamin C level and oxidative stress (8-iso-PGF2a isoprostane). All participants will be asked to return their respective supplementation bottles to the research assistant at Month 3. We will count pills to determine patient adherence to taking the placebo or vitamin C supplementation.

**Follow up phone call (Month 1 and 2).** Follow up phone calls will occur within 1 week after enrollment to follow-up whether they are taking the investigational pills (vitamin C or placebo) daily and whether they have any adverse events from taking the investigational pills, as well as at Month 1 and 2. The research assistant will inquire about general welfare and collect data on HF symptom burden and HRQOL (for both groups).

***Month 3 visit.*** Data on socio-demographics, clinical characteristics medications, symptom burden, PROMIS depression, fatigue, and sleep disturbance, HRQOL, will be collected at the beginning of the visit and blood will be drawn to measure serum vitamin C level and oxidative stress (8-iso-PGF2a isoprostane). All participants will be asked to return their vitamin C (or placebo) bottle to the research assistant at Month 3. We will count pills to determine their adherence to taking the placebo or vitamin C supplementation.

## 6. CONSENT PROCESS

The consent process includes: 1. Obtain written informed consent from the study subject; 2. Ensure that the most recent version of the IRB-approved consent/HIPAA authorization form is used; 3. Review the informed consent/HIPAA authorization form with the subject in a location that allows privacy; 4. Allow the subject time to read the document and ask questions. Encourage input from family members, if appropriate; 5. Ensure that the subject signs and dates the document in the required sections of the consent and HIPAA authorization form; 6. Ensure the consentor signs and dates (same date) the document in the required section of the consent form; 7. Provide a signed copy of the informed consent/HIPAA form document to the subject; and 8. Document and date consent procedure and file the signed document and checklist back to locked cabinet.

The data (from self-report, impedance cardiograph, and blood drawn) will be collected at baseline clinic appointment and Month 3 in person for all patients. HF symptom burden and HRQOL will be collected at baseline and Month 3, in person and also Month 1 and 2, by phone. All patients will be compensated up to \$50 for participating in this study: \$25 at baseline visit and \$25 at Month 3 visit.

Under special circumstances that we are not allowed to collect in-person data at Month 3 (such as Covid-19 pandemic stay-at-home order that prevents our in-person data collection), we will not collect data from impedance cardiograph or blood drawn. We will only collect self-report data using one of the following 2 ways based on subjects' preference: 1) by phone; 2) by mail-- we will send subjects the questionnaires ahead of time and ask them to complete and send the questionnaire back to us. We also will ask them to send their un-used vitamin C pills back to us by mail.

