The secondary endpoints are symptom burden, HRQOL, cardiac function, and oxidative stress. For Aim 2 to test the effect of a vitamin C supplementation intervention on the secondary endpoint of HF symptom burden from baseline to 3-month follow-up among 3 groups, we will use repeated measure of ANOVA to detect differences in symptom burden from baseline to 3-month follow-up in the intervention group and compared to the control group from baseline to 3-month follow-up. Similarly, to test the effect of a vitamin C supplementation intervention on the secondary endpoint of HRQOL (cardiac function, and oxidative stress) compared to the control group, we will use repeated measure of ANOVA to detect differences in HRQOL (cardiac function, and oxidative stress) from baseline to 3-month follow-up in the intervention group and compared to the control group from baseline to 3-month follow-up.

Similar analysis will be done for adverse events. to test the effect of a vitamin C supplementation intervention on the frequencies of adverse events compared to the control group, we will use ANOVA to compare frequencies of adverse events during the 3-month period among 3 groups.

Sample Size and Power: The total sample size of 42 participants will be selected as a pilot feasibility study. With 42 patients (14 in each group) and an alpha level of .05, the power of the ANOVA F test to detect a significant group difference will be 80% if the effect size is 0.5.

Interim/safety Analysis. We plan to conduct the interim/safety analysis when we have 50% of the intervention sample, and the findings (as well as adverse events) will be reported to the medical monitor. The medical monitor will make decisions about the safety of continuing (or stopping) the protocol, providing recommendations for recruitment, retention, safety, and other issues as appropriate.

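### A patient who cannot attend at any time in the Month 3 window has no stated phone or mail route to a Month 3 symptom burden, HRQOL or PROMIS score

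*Combined protocol and SAP*

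**What the plan says.** Section 6 (Consent Process) sets the default. Self-report, impedance and blood data "will be collected at baseline clinic appointment and Month 3 in person for all patients". For the two questionnaires that matter here it says: "HF symptom burden and HRQOL will be collected at baseline and Month 3, in person and also Month 1 and 2, by phone".

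The exception follows in the same section: "Under special circumstances that we are not allowed to collect in-person data at Month 3 (such as Covid-19 pandemic stay-at-home order" is the condition, and then "We will only collect self-report data using one of the following 2 ways based on subjects' preference: 1) by phone; 2) by mail". The stay-at-home order is only an example, but the condition it illustrates is a bar on the study team, not a patient's own inability to come.

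Section 4 (Intervention) gives the timing: "with some flexibility to do the final visit at 3 months +/- 1 month) coordinated with their regular clinic visits". Section 5 describes Month 3 only as a visit, with the questionnaires, including PROMIS depression, fatigue and sleep disturbance, completed at its start. Section 3 confirms the telephone practice earlier in follow-up: "HF symptom burden and HRQOL will also be measured at Month 1 and 2 by phone".

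Section 9 analyses symptom burden by repeated-measures ANOVA to "detect differences in symptom burden from baseline to 3-month follow-up", and treats HRQOL the same way. It gives no rule for a missing Month 3 score.

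**The concern.** The Aim 2 comparison of symptom burden and HRQOL needs a Month 3 score. Read literally, the remote procedure cannot be used for a patient who is in hospital for a long time, too unwell to travel or otherwise out of reach in person throughout the window. The research assistant already takes both instruments by phone at Months 1 and 2, so the plan gives up scores that it has the means to collect.

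Such losses are unlikely to be random. Section 1 links symptoms to frequent hospitalization and reduced HRQOL, and section 7 reports a relationship between HRQOL and re-hospitalization or mortality. Patients who cannot attend may well be among those with the worst scores. Section 3 says that the pilot is meant to supply initial effect-size estimates for a later RCT, so illness-related gaps in two of the secondary endpoints touch a stated purpose of the study.

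**Working it through.** **1. Is there a remote route elsewhere?** Four places bear on this:
- Section 3: phone collection is set for Months 1 and 2.
- Section 4: the final visit may fall at 3 months ± 1 month.
- Section 5: Month 3 is a visit.
- Section 6: in person for all; phone or mail only if the study is not allowed to work in person.

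None covers an individual who cannot attend within the window. Months 1 and 2 phone scores would exist for such a patient, but they are not Month 3 scores. The text does not say whether Months 1 and 2 enter the ANOVA; in complete-case form the patient is dropped either way.

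**2. The plan's own power figure.** Inputs from section 9: 42 patients, three groups of 14, alpha 0.05, effect size 0.5, power 80%. The metric is not named; Cohen's f reproduces the figure. Noncentrality = N × f² = 42 × 0.25 = 10.5 with 2 and 39 degrees of freedom, giving power 80.3%.

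**3. Precision.** The documents give no missed-visit rate, so a loss of 1 to 4 of 42 is assumed. Standard errors scale with √(42/n):
- 1 lost: √(42/41) = 1.012, about 1% wider; power at f = 0.5 is 79.2%.
- 4 lost: √(42/38) = 1.051, about 5% wider; power at f = 0.5 is 75.6%.

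**4. Bias, one assumed scenario.** Month 3 scores (higher is worse) are N(0, 1) on placebo and N(−0.5, 1) on active treatment. In both arms half of the scores above a common cut c are missing, with c = z(1 − 2p), so that a fraction p of placebo patients is lost. With a = c − μ, the observed mean in an arm is

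[μ − 0.5 × (μ × (1 − Φ(a)) + φ(a))] / [1 − 0.5 × (1 − Φ(a))].

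For p = 0.10, c = 0.842:
- Placebo: −0.5 × 0.280 / 0.90 = −0.156.
- Active: a = 1.342, 1 − Φ(a) = 0.090, φ(a) = 0.162; (−0.5 − 0.5 × 0.117) / 0.955 = −0.585.
- Difference: −0.585 + 0.156 = −0.429.

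| Placebo loss p | Active loss | Expected loss of 42 (14 placebo, 28 active) | Observed difference | Shrinkage |
|---|---|---|---|---|
| 5% | 1.9% | 1.2 | 0.449 SD | 10% |
| 10% | 4.5% | 2.7 | 0.429 SD | 14% |
| 20% | 11.3% | 6.0 | 0.428 SD | 14% |

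The first two rows lie within the range of 1 to 4 lost; the third goes beyond it.

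**5. The sign can reverse.** Keep placebo complete and let half of the worst fifth of an active arm be missing. By the same arithmetic the active mean moves by −0.156, to −0.656, and the observed difference grows from 0.50 to about 0.66 SD.

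**6. Scale.** The standard error of a 14-versus-14 difference is √(2/14) = 0.38 SD. The shifts in the table, 0.05 to 0.07 SD, are less than a fifth of that.

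**The case against.** The best reply is that the gap is narrow, and much of it stands.

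- A reader might infer that anyone who is ill, in hospital or off the clinic schedule has no route at all to a Month 3 score. The documents do not support that. The window spans two months and a 4-month supply is dispensed, so a short illness, a brief admission or a moved appointment can still end in an in-person score.
- A reader might also infer that the study visit depends on a routine appointment. Section 4 only says that it is "coordinated with their regular clinic visits that are typically scheduled every 3 months"; nothing cancels the study visit if the appointment moves. Section 6 asks only for in-person collection at Month 3, and the impedance device is portable, so seeing an inpatient is not excluded.
- It is tempting to quote a larger bias. If every placebo score in the worst 5%, 10% or 20%, and every active score above the same cut, were missing, 0.50 SD would fall to 0.43, 0.39 or 0.33 SD (14%, 22% or 34%). That arithmetic is right, but it needs complete loss above a fixed score and none below it, and no document supports such a pattern.
- It is also tempting to say that the bias runs toward no effect. That presumes that vitamin C works and that only poor health causes absence. Section 8 lists digestive complaints among possible adverse events of the pills, and these could cause loss in the active arms instead.
- The 50% readmission figure in section 1 concerns patients after discharge. This sample is more than a month from any admission, on optimized therapy, and excludes NYHA class IV and stage D, so that figure gives no missed-visit rate here.
- Retention and attrition are themselves Aim 3 outcomes, and the primary endpoint gains nothing from remote self-report.

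None of this supplies a remote route for the patient who cannot be seen in person at any time in the window.

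**Conclusion.** The point holds in a limited form. As written, remote Month 3 self-report depends on the study being barred from in-person work, and a patient who is personally unable to attend throughout the window is not covered. The number affected is unknown and probably small.

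The precision figures (standard errors about 1–5% wider) rest on an assumed loss of 1 to 4 of 42. The 10–14% shrinkage rests on an assumed 0.50 SD effect, normal Month 3 scores analysed without baseline, and one-sided loss of half the scores above a common cut. It illustrates size and is not a forecast; the direction of any bias cannot be settled in advance. All of this assumes a complete-case analysis, which the plan neither states nor rules out.

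This is a cheap improvement to the collection of two secondary endpoints and the PROMIS measures, not a fault that undermines the design.

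**What to change.** In section 6, widen the condition for remote collection. Any participant who cannot attend in person within the 3 months ± 1 month window, for whatever reason, should give symptom burden, HRQOL and PROMIS by the phone or mail procedure already described there. Record the reason for non-attendance and the mode. In section 9, state that remotely collected symptom burden and HRQOL scores enter the Aim 2 analysis, and check the effect of mode in a sensitivity analysis.

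The cost is about a sentence in each section and a few calls or mailings by the same research assistant. The downside is that some Month 3 scores come by a different mode from baseline. The plan already accepts this for periods when in-person work is barred, and it already uses the phone for symptom burden and HRQOL at Months 1 and 2. PROMIS is not scheduled by phone at those months, so its mode deserves the closer look.

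The change does not recover serum vitamin C, cardiac output or isoprostane, which still need an in-person visit.
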